2.2 Secondary Objective(s)

Aim 2: Determine the differences in ostomy-related **medical care utilization** and family **financial burden** imposed on survivors between OSMT and UC groups.

Hypothesis 2.1: OSMT telehealth subjects will use fewer **ostomy-specific family resources** in the 6 months after OSMT compared to UC subjects.

Hypothesis 2.2: OSMT telehealth subjects will use fewer **ostomy-specific health care services** in the 6 months after OSMT compared to UC subjects.

Question 2.1: What is the difference in the overall levels of **ostomy-related family financial burden** between OSMT and UC groups?

Question 2.2: What are types and levels of effort of OSMT intervention personnel and specific equipment, supplies, and informatics support required to implement and operate a successful OSMT program; what are participants' levels of use of ostomy-specific health care services and supplies; and what are the time and in-home requirements for participating in OSMT for survivors and their family caregivers. This information is required for replicating our OSMT intervention in the event that we find it improves the primary and secondary outcomes of OSMT participants.

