The focus of Aim 2 is to compare medical care utilization, patient burden, and impact on patient time and activities for individuals participating in OSMT with those receiving UC. Assessment of these measures is critical for patient-centered care, in order to minimize the financial burdens and non-financial impacts (e.g., time commitment) of new interventions. To address hypotheses 2.1 and 2.2, we will collect detailed information on use of medical care services and supplies related to ostomy care, patient burden for these services and supplies, required patient and caregiver time for ostomy care, interference with employment and volunteer activities, and perceived financial burden. Details regarding the four types of information to be collected for Aim 2 are presented below. We also provide information on assessment on study activities to address replication of the OSMT intervention (Question 2.2).

12.4 Ostomy-Related Medical Care Supplies and Services. We will collect information from study participants on their use of supplies and services related to ostomy care and their out-of-pocket expenses for these supplies/services. Ostomy-related services/supplies will be categorized in two separate groups:

- Medical care encounters and ostomy supplies including: OCN visits; other ostomy-related medical care encounters (including physician and ED visits); surgical revision of stoma; ostomy appliances, wafers, bags; bowel medications; and skin medications.
- Other equipment, household modifications related to ostomy and ostomy care, including: waterproof covers on for mattresses and furniture; bathroom remodels to accommodate ostomy care; special clothing to cover ostomy bag; alteration of clothing to cover ostomy bag, and transportation to and parking for ostomy-related medical care.

12.5 Ostomy-Related Time Requirements. We will also collect ostomy-related time requirements, that is, patient time required to obtain ostomy care, perform ostomy bag and wafer management, and clean ostomy bag spills. We will also ask study participants about use of both formal and informal CGs, time for caregiving activities related to ostomy care, and types of assistance (e.g., with housekeeping and shopping) required due to ostomy and ostomy care.

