3. Skin Adhesive Removers
 - a. Used to remove adhesive after applying the wafer and pouch (Not recommended for routine use)
 - b. Some ostomates find it easier to reapply wafer if some adhesive is left on the skin
4. Deodorizers
 - a. Used to reduce odor
 - b. Tablet form you eat or drop into pouch
 - c. Vents are also available to apply to pouch to release gas and deodorize it as it passes through the vent
5. Stoma Patches and Caps
 - a. Used to prevent leakage when colostomy is irrigated and stool is controlled
 - i. Pouch Covers: A cover that goes around your pouch to absorb sweat and to cover the contents of the pouch

- ii. Convexity
 - a) Skin irritation can occur from leakage on the skin
 - b) Use of convex wafer makes the stoma protrude from skin and redirects flow of urine or feces into pouch
- 6. Pouches
 - a. One Piece System
 - i. The wafer and pouch are attached as one unit
 - ii. Advantages
 - a) Quick and easy to use
 - b) Less Bulky (One vs. Two Parts)
 - b. Two-Piece System
 - i. The wafer and pouch are two separate pieces and are attached by attaching the wafer connector to the pouch connector
 - ii. Advantages
 - a) Can change bag size for different moments
 - b) Easier to relieve gas
 - iii) Disadvantage
 - a) Since attached wafer to bag, error may occur causing leakage
 - b) May be difficult to attach wafer to pouch and abdomen if ostomate is visually impaired
- 7. Belts
 - a. Some ostomates prefer to wear a belt
 - i. Attach to wafers using a special tag
- 8. Daily Care
 - a. Colostomy bag should be emptied when reaches 1/3 gas or stool
 - i. Achieve pouch adherence up to 5 days
 - b. If you use the reusable pouches, make sure they are thoroughly cleaned with mild soap and water
- 9. Disposal of ostomy bag
- 10. Reviewing Routines
- 11. Emergency Kits

Session 1 Assignments (5 min)

C. Assignments

1. Goal Development for Session 2

When you completed the first survey packet, it contained a goal development sheet. We are now going to ask you to please describe the goals you have in regards to your ostomy care.

2. Monitoring timed daily outputs/Nutrition Log by Time

Please monitor your daily bowel movements and how they are affected by different situations or foods. These will be discussed at upcoming sessions and will be useful if issues were written down.

Session 1 Resources (5 min)**D. Resources**

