Please answer questions 13c through 13f thinking specifically about your most recent Urgent Care visit for stoma and/or bowel function problems.

- c. How much did you pay out-of-pocket for your most recent Urgent Care visit (copayments, deductibles, or other costs for the visit that weren't covered by your insurance)?
 \$0 \$1-\$5 \$6-10 \$11-15 \$16-\$25 \$26-\$50 \$51-\$100 \$101+
 d. How much did you pay out-of-pocket to get to and from the Urgent Care visit (such as the cost for taxi, bus, or parking)? \$0 \$1-\$5 \$6-10 \$11-15 \$16-\$25 \$26-\$50 \$51-\$100 \$101+
 e. Approximately how far did you have to travel to the Urgent Care visit location? 1-4 miles 5-8 mi. More than 8 mi.
 f. Approximately how much time did it take you to get from your home to the Urgent Care visit location? 1-4 minutes 5-8 min. More than 8 min.

14. What type of ostomy bag system are you using? One piece Two piece

15. How many of each of the following have you used over the past 4 weeks?

- a. Wafers: 10 or less 11-20 21-30 31-50 More than 50
 b. Bags: 10 or less 11-20 21-30 31-50 More than 50

16. Medications to manage your bowel function in the past 4 weeks

- a. Have you used any medications to manage your bowel function in the past 4 weeks? (e.g., Imodium®, Metamucil®, Miralax®, Loperamide) No (IF NO, skip to Question 16. below.) Yes
- b. **IF YES:** how many different medications have you used to manage your bowel function in the past 4 weeks? ____
- c. Please list up to three medications you used most frequently to manage your bowel function and the number of days you took these medications in a typical week:
 - i. Medication _____ Number of days used (0 to 7) _____
 - ii. Medication _____ Number of days used (0 to 7) _____
 - iii. Medication _____ Number of days used (0 to 7) _____

17. Do you use the Eakin seal (moldable donut or ring)? No Yes

18. Medications to manage – treat or prevent – skin problems around your stoma in the past 4 weeks

- a. Have you used any prescription medications to manage skin problems around your stoma in the past 4 weeks? (e.g., Nystatin powder). No (IF NO, skip to Question 18. below.) Yes
- b. **IF YES:** how many different medications have you used to manage skin problems around your stoma in the past 4 weeks? None 1-2 3-4 5 or more
- c. Please list up to three medications you used most frequently to manage skin problems around your stoma and the number of days you took these medications in a typical week:

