 - i. Medication _____ Number of days used (0 to 7) _____
 - ii. Medication _____ Number of days used (0 to 7) _____
 - iii. Medication _____ Number of days used (0 to 7) _____

19. How much have you spent on purchases of ostomy appliances (including wafers and bags in total over the past 4 weeks)? \$0 \$1-\$25 \$26-50 \$51-100 \$100-\$150 \$150-\$200 \$200-\$250 over \$250

20. About how many times a day do you empty your drainable ostomy bag (or discard your closed/disposable bag)?

- None 1-4 5-8 More than 8

21. Over the past 4 weeks, what was the highest number of bag emptyings in a 24-hour period?

- None 1-4 5-8 More than 8

22. Over the past 4 weeks, what was the lowest number of bag emptyings in a 24-hour period?

- None 1-4 5-8 More than 8

23. How often do you typically discard a used bag and use a new bag?

- At every emptying Once a day Once every 2-3 days Less often

24. How much time does it usually take you to empty/dispose your bag?

- 1-5 minutes 5-10 minutes 10-15 minutes More than 15 minutes

25. How often do you typically change your wafer on a typical week? 1 2 3 4-7 More than 7

26. How much time does it usually take you to change your wafer and bag?

- 1-15 minutes 16-30 minutes 30-45 minutes 45-60 minutes More than 60 minutes

27. Do you usually receive help caring for your stoma and changing your ostomy appliance?

- a. No (skip to Question 27 below)
- b. Yes IF Yes, please check who your helper(s) is(are):
 Spouse/Significant Other Other family member Friend Home care nurse Other Paid Caregiver Other (please specify) _____

28. Has your bag leaked at any time over the past 4 weeks?

- a. No (skip to Question 28 below)
- b. Yes **IF YES**, how many times? 1-4 5-8 More than 8
- c. How many of these times involved a full spillage of your bag contents? 1-4 5-8
More than 8
- d. How much time does it require to clean up after a bag leak or spill? 1-30 minutes 31-60 mins.
More than 60 mins

29. Do you have waterproof covers on your mattress and primary chair(s)?

- a. No → Skip to Question 29 below.
- b. Yes **IF YES**, how much did you spend to purchase them?
\$0 \$1-\$10 \$11-\$25 \$26-\$50 \$51-\$75 \$76-\$100 \$101-\$150 \$151+

30. Do you have to make alterations to your clothing to accommodate your ostomy appliance?

- a. No **IF NO**, skip to Question 30 below.
- b. Yes **IF YES**, do you make these modifications yourself?
 - i. No
 - ii. Yes → **IF YES**, How much do you spend for these modifications?

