15.7 Appendix 7b Burden of Ostomy Care Survey (short survey, after session completion)

BURDEN OF OSTOMY CARE: CHECK-IN REPORT

This study aims to collect information on families' use of ostomy care and supplies, including ostomy-related medications, and ostomy-related health care visits. We ask that you please answer these questions while thinking specifically about your *ostomy-related care*. This is not a test. Please give us your best estimates based on your personal experience.

1. In-person Visits with Wound and Ostomy Care Nurse in the past 4 weeks:

- a. Did you visit a Nurse in person in the past 4 weeks (at a medical office, hospital, and/or in your home)? No (**IF NO**, skip to Question 3. below.) Yes
- b. **IF YES:** How many times did you visit the Nurse in the past 4 weeks? 1 2 3-4
 5-8 More than 8

2. Telephone and/or email consultations with a Wound and Ostomy Care Nurse in the past 4 weeks:

- a. Did you have any telephone and/or web consultations with the Nurse in the past 4 weeks? No (**IF NO**, skip to Question 4. below.) Yes
- b. **IF YES:** How many telephone and/or web consultations have you had with a Wound and Ostomy Care Nurse over the past 4 weeks? 1 2 3-4 5-8 More than 8

3. In-person Visits with a Physician for stoma and/or bowel function problems in the past 4 weeks:

- a. Did you visit a Physician in person for stoma and/or bowel function problems in the past 4 weeks? No (**IF NO**, skip to Question 5. below.) Yes
- b. **IF YES:** How many times did you visit the Physician in the past 4 weeks?
 1 2 3-4 5-8 More than 8

4. What other sources do you use to find more information about your ostomy and daily care? (Fill in all that apply)

- Internet Magazines Other people with an ostomy Support Group
- Other (please specify)

5. If you wear a pouch and have encountered any problems with it, please explain below what those problems are/were?

6. Do you feel comfortable with your daily ostomy care? Yes No
7. On average, how long does it take to do your daily ostomy care?
 0-5 min 5-10 min 10-15 min 15-30 min 30-60min More than 60 min
8. How often do you typically discard a used bag and use a new bag?
 At every emptying Once a day Once every 2-3 days Less often
9. How often do you typically change your wafer on a typical week?
 1 2 3 4-7 More than 7
10. How much time does it usually take you to change your wafer and bag?
 1-15 minutes 16-30 minutes 30-45 minutes 45-60 minutes
 More than 60 minutes

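### Item 15a of the burden survey puts every wear time the study mentions into its lowest wafer band, so by itself it can barely show a difference in wafer use; item 25 recovers most of it

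*Protocol*

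**What the plan says.** Protocol 12.4 lists "ostomy appliances, wafers, bags; bowel medications; and skin medications" among the supplies for which use is collected under Aim 2. Question 2.2 (Protocol 2.2) asks "what are participants' levels of use of ostomy-specific health care services and supplies".

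The instrument is the Burden of Ostomy Care survey. The full form (Appendix 7a) is given at baseline and at the 6-month follow-up, and a short form (Appendix 7b) after the sessions (Protocol 8.2). Item 15 of the full form asks "How many of each of the following have you used over the past 4 weeks", with these options for wafers: "Wafers: 10 or less 11-20 21-30 31-50 More than 50". Item 15b offers the same bands for bags.

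Item 25 of the full form approaches wafer use in another way: "How often do you typically change your wafer on a typical week? 1 2 3 4-7 More than 7". Item 9 of the short form repeats that question. Items 19 and 23 of the full form record spending on appliances and how often a bag is replaced.

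Two places in the study materials mention wear time. The Session 1 curriculum says "Achieve pouch adherence up to 5 days". Item 5 of the knowledge survey (Appendix 6) offers an interval of 4 to 7 days as one answer option; no answer key is given.

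**The concern.** Longer wear, and so fewer wafers, is a direct way in which self-management training could reduce family resource use (Hypothesis 2.1, Question 2.1). Item 15a is the natural variable for an analyst who follows Protocol 12.4, because it asks how many wafers were used in a defined period. If most participants in both arms tick the lowest band at both surveys, that variable will show little difference whatever the intervention does. A report of no difference in wafers used could then reflect the response options rather than behaviour. Neither the Protocol nor the SAP says which item is the measure of wafer use.

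**Working it through.** There is no document figure to reproduce: no expected level, test or power is stated for wafer use.

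**Step 1: what the lowest band covers.** Wafers per 4 weeks = 28 / wear time in days. The band limit of 10 corresponds to 28/10 = 2.8 days.

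| Mean wear (days) | Wafers per 28 days | Item 15a band |
|---|---|---|
| 2.5 | 11.2 | 11-20 |
| 2.8 | 10.0 | 10 or less |
| 3 | 9.3 | 10 or less |
| 4 | 7.0 | 10 or less |
| 5 | 5.6 | 10 or less |
| 7 | 4.0 | 10 or less |

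A participant who goes from 9 wafers to 4, a fall of (9 - 4)/9 = 56%, gives the same answer to item 15a.

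**Step 2: what item 25 records.** Multiplied by 4 weeks, its options of 1, 2, 3 and 4-7 changes per week stand for about 4, 8, 12 and 16-28 wafers; the top option is more than 28. The fall from 9 to 4 is 9/4 = 2.25 to 4/4 = 1 change per week, so the answer moves from 2 to 1.

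**Step 3: how much this matters for a comparison of arms.** The documents give 75 completers per arm and alpha 0.05 (Protocol 12.13). Everything else here is assumed: lognormal wear time, wear 15% longer in one arm, a Mann-Whitney test, and two-sided testing (the documents do not state the sidedness). A coefficient of variation (CV) of 0.3 or 0.5 gives a log-SD of sqrt(ln 1.09) = 0.29 or sqrt(ln 1.25) = 0.47. With 1,500 simulations per row, the Monte Carlo standard error is at most sqrt(0.25/1500), about 1.3 points.

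| Median wear (days) | CV | In lowest band of 15a | Power: count | Power: item 15a | Power: item 25 |
|---|---|---|---|---|---|
| 3 | 0.3 | 66% | 81% | 57% | 72% |
| 3 | 0.5 | 60% | 44% | 31% | 40% |
| 4 | 0.3 | 92% | 81% | 24% | 70% |
| 4 | 0.5 | 81% | 40% | 21% | 35% |
| 5 | 0.3 | 98% | 81% | 3% | 60% |
| 5 | 0.5 | 91% | 43% | 15% | 33% |
| 6 | 0.3 | 100% | 81% | 0% | 45% |
| 6 | 0.5 | 96% | 42% | 9% | 26% |

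Across the wider grid (median 3 to 6 days, log-SD 0.25 to 0.47) the ranges are 60-100% in the lowest band, and power of 38-92% with a count, 0-71% with item 15a and 26-84% with item 25. Splitting the lowest band as proposed below recovers nearly all of the loss.

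**Step 4: bags.** The curriculum describes a one-piece system as wafer and pouch in a single unit. For a drainable one-piece system the bag count therefore equals the wafer count, and item 15b has the same weakness. Item 23 does not resolve it, because its last option pools everything less frequent than every 2-3 days.

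**The case against.** A reader might infer that a difference in supply use between the arms would be largely invisible in this trial. The documents do not support that. Item 25 separates users within the range that item 15a pools, and it is asked at baseline and follow-up. The short form repeats it after the sessions, so weekly wafer changes are available at all three surveys, which is more often than item 15. Spending (item 19) and bag replacement (item 23) add to this. At a median wear of 3 to 4.5 days item 25 keeps most of the power of a count. This part of the objection stands.

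A reader might also infer that nearly every participant will tick the lowest band. The wear times come from a teaching goal and a quiz option, not from observed use. Training can start six weeks after surgery (Protocol 5.1), and participants with leaks or skin problems may change more often. With a median of 3 days, 34-40% would be above the band. So the share is an assumption, and the loss from item 15a shrinks when wear is shorter or more variable.

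Finally, no between-arm test of wafer counts is specified. The rank test and the 15% effect are illustrative, and Question 2.2 is descriptive.

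What survives is narrower. Item 25 refers to a typical week rather than the past 4 weeks, does not cover bags, and has no option below once a week, so it loses more at about 6 days. No text names it as the measure of wafer use. A description of levels of use also suffers if most answers sit in one open band.

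**Conclusion.** The point holds for item 15a, and for item 15b with one-piece drainable systems. At every wear time the study materials mention, use is 4 to 7 wafers per 28 days and falls in a single band. At assumed medians of 4 to 6 days with 15% longer wear, item 15a has 0-24% power in the table above, against 40-81% for a count. At a median of 3 days it does better (31-57% in the table), so the size of the loss depends on a distribution that the documents do not give. It does not hold for the survey as a whole, because item 25 carries most of the information at 3 to 4.5 days, with a larger loss at about 6 days. Importance is minor: one component of secondary Aim 2, with no test or power stated for it. The arithmetic on the bands is certain; the power figures are illustrations under stated assumptions.

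**What to change.** In Appendix 7a item 15, either ask for the number used over the past 4 weeks or split the lowest band. For wafers the bands could be 0-3, 4-5, 6-7, 8-10, 11-15, 16-20 and more than 20. For bags, split the low end in the same way but keep the upper bands, since item 23 allows for a new bag at every emptying. State in the SAP that, for forms already returned, the between-arm comparison of wafer use is taken from item 25 and not from item 15a.

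The cost is one edited question in the paper and RedCap forms and one sentence in the SAP. A fill-in number brings some rounding in recall. Participants surveyed before the change have only the banded item 15 at baseline, so a baseline-adjusted analysis of the new item is not possible for them; any comparison that includes them should use item 25. If the form can no longer be changed, naming item 25 as the wafer-use measure costs nothing and removes most of the problem.

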 - iii. Urostomy (typically known as an Ileal Conduit)—created when bladder has been removed. A small piece of small intestine (ileum) is surgically removed and used as a conduit. Occasionally large bowel is used. The two ureters from the kidneys are attached to this piece of ileum creating the conduit. The one end of bowel is sutured closed and the other end of the conduit is brought out through the abdominal wall creating the stoma.

2. Characteristics of a healthy stoma.

- a. Stoma is not painful. It has no nerve endings.
- b. Always red and moist.
- c. May bleed easily.

3. Associated diseases that can lead to an intestinal ostomy

- a. Cancer – the focus of this program
 - i. Rectal Cancer
 - ii. Colon Cancer
 - iii. Other cancers
 - a) Inflammatory Bowel Disease
 - b) Diverticulitis
 - c) Injury

4. Associated diseases that can lead to a urinary ostomy

- a. Bladder Cancer - the focus of this program
- b. Injury

5. What type of ostomy do you have?

- a. What is your understanding of your ostomy?
- b. What are your goals as an ostomate (person with an ostomy)?
- c. An ostomy may be temporary or permanent. Which do you have?
- d. How do you feel about your ostomy?

6. Be familiar with how you react to different appliances/pouches and certain foods

7. If your ostomy supplies make you feel uncomfortable, try another pouching system

8. Clothing
 - a. Immediate changes after surgery, but once healed the optimal goal is to be in pre-operative clothing
 - b. Must be recognized that you may not feel comfortable with old clothing
 - c. New clothing options
 - i. Suspenders
 - ii. Loose fitting clothes
 - iii. Overalls
 - vi. Specialized clothing <http://www.securicaremedical.co.uk/clothing-for-ostomates.asp>
9. Effects of Nutritional Intake
 - a. Foods or types of foods affect everyone differently, so it is important to determine certain foods to avoid or not eat before certain occasions
 - i. Examples: Spicy foods, nuts, and seeds
 - ii. Food or types of foods that are helpful
 - iii. Plenty of fluids (water or juices), particularly in ileostomate and urostomate

Session 1 Equipment Skills Lab (30 min.)

B. Skills Lab

We recognize many people are not comfortable with ostomy supplies yet. This part of the session is to review current and other possible options available in the future.

1. Checking out the equipment: Appliances, Pouches, Belts
2. Skin Preps: Helps lengthen wear time of wafer and pouch, and prevents skin irritation

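### The burden survey asks no cost for bowel or skin medications and admits only prescription skin medications, although section 12.4 plans out-of-pocket expenses for both without that limit

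*Protocol*

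**What the plan says.** Section 12.4 of the protocol plans to collect participants' "use of supplies and services related to ostomy care and their out-of-pocket expenses for these supplies/services". The first of its two groups combines medical encounters with supplies and ends with "ostomy appliances, wafers, bags; bowel medications; and skin medications". It does not limit skin medications to prescribed ones.

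The question these data serve is Question 2.1 (section 2.2): "What is the difference in the overall levels of ostomy-related family financial burden between OSMT and UC groups". Hypothesis 2.1, on ostomy-specific family resources, also draws on them.

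The instrument is the Burden of Ostomy Care survey, Appendix 7a, given at baseline and at the 6-month follow-up (section 8.2). Its relevant items are:

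- Item 16, bowel medications. After a yes/no entry question it asks "how many different medications have you used to manage your bowel function in the past 4 weeks", then names and days of use per week. It asks no amount.
- Item 18, skin medications. The heading covers both treatment and prevention. The entry question 18a is "Have you used any prescription medications to manage skin problems around your stoma in the past 4 weeks". A Yes leads to number, names and days of use. It asks no amount.
- Item 19, spending: "How much have you spent on purchases of ostomy appliances (including wafers and bags in total over the past 4 weeks". Answers are in bands.

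The Session 1 skills lab in Appendix 1, delivered to the OSMT arm, lists "Skin Preps: Helps lengthen wear time of wafer and pouch, and prevents skin irritation".

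**The concern.** The form does not deliver a quantity that section 12.4 says will be collected. Two separate losses follow.

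1. **Cost.** No medication spending is recorded, so an arm comparison of supply spending rests on appliances alone.
2. **Use.** Question 18a turns away people whose only skin products are non-prescription, so use of skin products is undercounted.

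An equal undercount in both arms would largely cancel from the absolute difference. There is a specific reason why it might not be equal. If OSMT participants take up skin preps and change wafers less often, the form can register lower appliance spending while missing the added skin-product spending. That shift would arise after randomization, so baseline adjustment would not remove it. At stake is the interpretation of one secondary-aim question.

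**Working it through.** The plan states no figure for this point, so there is nothing to reproduce. The check compares the plan with the form and then gives an illustration under assumed prices.

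**Step 1. Plan against form.**

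| Supply named in section 12.4 | Use recorded in 7a | Out-of-pocket amount recorded in 7a |
|---|---|---|
| Appliances, wafers, bags | Items 15, 23, 25 | Item 19 |
| Bowel medications | Item 16; examples include Imodium and Metamucil | None |
| Skin medications | Item 18, entered by prescription only | None |

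The gap stands out because 7a does ask for dollars elsewhere: nurse and physician visits and consultations, travel, emergency and urgent care, waterproof covers, clothing, accessories and hernia belts. The interim form, Appendix 7b, has no medication or cost item, so it does not fill the gap.

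**Step 2. Who is lost at 18a.** A No leaves the block. (The printed skip target is the item's own number; I read it as the next item.) Parts 18b and 18c do not repeat the prescription limit.

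- Non-prescription products only: answers No and is recorded as a non-user.
- Both kinds: answers Yes and can list both.
- Prescription only: recorded.

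The loss is therefore confined to the first group. Item 17 records use of one moldable seal regardless of prescription, but only as Yes or No, without cost.

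**Step 3. Could spending shift? (assumed prices)** The documents give no prices or wear times by arm. Assume 5 to 10 dollars per wafer-and-bag set.

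Appliance spending per 28 days = (28 / wear days) × price per set.

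True saving = fall in appliance spending − added skin-product spending.

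- Wear rising from 3 to 5 days: sets fall from 28/3 = 9.3 to 28/5 = 5.6. At 5 dollars, spending goes from 47 to 28, a fall of 19. At 10 dollars, it goes from 93 to 56, a fall of 37.
- Wear rising from 4 to 5 days: sets fall from 7.0 to 5.6. The fall is 7 dollars (35 to 28) or 14 dollars (70 to 56).

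| Added skin-product spending | True saving, 3 to 5 days, 5 / 10 dollars a set | True saving, 4 to 5 days, 5 / 10 dollars a set |
|---|---|---|
| 0 | 19 / 37 | 7 / 14 |
| 10 | 9 / 27 | −3 / 4 |
| 20 | −1 / 17 | −13 / −6 |
| 40 | −21 / −3 | −33 / −26 |

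Depending on the assumptions, an apparent appliance saving can be real, overstated, or hide a net loss.

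**Step 4. What item 19 would register.** Its bands in this range are 26–50 and 51–100 dollars. All four falls above stay inside one band: 47 to 28 and 35 to 28 in the lower, 93 to 56 and 70 to 56 in the upper. For the change from 3 to 5 days, the answer would cross the edge at 50 dollars only at set prices between about 50/9.33 = 5.4 and 50/5.6 = 8.9 dollars. So even a real appliance saving may not show for a given participant, and the exact-dollar illustration is not what the form would report.

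**The case against.** A reader might infer that the survey is biased in favour of OSMT. The documents do not support that, for these reasons:

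- **The curriculum pulls both ways.** It says adhesive removers are not for routine use, which could lower unrecorded spending. It suggests trying another pouching system and presents convex wafers and two-piece systems, which could raise item 19 spending. Fewer skin problems could also reduce skin-product purchases, a saving the form would miss.
- **Usual care is also prompted on skin care.** Section 9.1 gives it a skin-care booklet with instructions and ostomy nurse contacts. OSMT receives these too, so only the skills lab and sessions differ. This softens the contrast without removing it.
- **Item 19 says including, not only.** Some respondents may count skin preps as appliances. That would shrink the omission, but answers would then mix two definitions.
- **Preps may not be medications.** Section 12.4 names skin medications, and preps and barriers are arguably something else. That narrows the prep argument. It does not explain the missing cost for medications or the prescription limit.
- **No total-dollar outcome is defined.** Neither sections 12.3 to 12.7 nor the SAP sets one, and Question 2.1 carries no directional hypothesis. Section 12.7 also plans a perceived-burden measure, whose items do not appear in 7a as available. It might reflect such spending, but it would not supply an amount.

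One defence fails. Section 12.10 declines to collect incurred expenses, but it concerns the inputs needed to run the intervention, not what participants pay.

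The 7a text may be incomplete at its end: the greatest-challenge question that section 8.2.3 places there is not shown. Items 16 to 19 are contiguous and complete, so the mismatch within them is not an extraction effect.

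**Conclusion.** The point holds as a mismatch between section 12.4 and Appendix 7a. As written, the form cannot yield the bowel- and skin-medication expenses that the plan says it will collect, and it records people who use only non-prescription skin products as non-users. This part needs no assumption beyond there being no catch-all spending item in the unseen end of 7a.

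A difference between arms is a possibility only. The mechanism is documented for skin products; for bowel medications the gap is simply a missing cost. Its direction and size cannot be found from the documents.

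Two further readings should be resisted:

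- A reader could assume 10 to 40 dollars of medication and skin-product spending against 50 to 100 dollars of appliance spending and find 10/(10+100) = 9% to 40/(40+50) = 44% unrecorded. That is a share of the spending level under invented amounts, and it does not measure bias between arms.
- The form does not lose every user of non-prescription skin products, because those who also use a prescription product pass 18a and can list both.

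The consequence is limited to Aim 2: the supply-spending part of Question 2.1, the spending part of Hypothesis 2.1, and the skin-medication use comparison. The primary PAM analysis is unaffected. The change is worth making because it is small and restores a quantity the plan promises.

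**What to change.** 1. In 18a, ask about prescription and non-prescription medications and skin products as two separately recorded answers. Keeping the prescription answer distinct preserves comparability with forms already completed.
2. Add a past-4-weeks out-of-pocket line to items 16 and 18. Use non-overlapping bands; item 19's own bands overlap at 100, 150 and 200 dollars and should not be copied.
3. State in item 19 whether skin preps and seals are included, and assign each product to one spending line so that nothing is counted twice.
4. Define in section 12 and the SAP that arms are compared on total supply and medication spending, with appliance spending as a component.

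The cost is a slightly longer form. If enrolment has begun, the new items will be missing from earlier baselines, so comparisons using them would rest on follow-up values or on later enrollees, and a clarified item 19 may not mean quite the same as before. For data already collected, no rewording helps: report item 19 as appliance spending only, not as total supply spending, and report item 18 as use among those who take at least one prescription skin medication.
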